4. SELECTION AND ENROLLMENT OF PARTICIPANTS

4.1 Inclusion Criteria

Subjects must meet all of the following inclusion criteria to be eligible for enrollment in the study:

- Diagnosed COVID+ status by physician, official testing site, or on-site rapid antigen test administered by study personnel at the time of visit. Either became symptomatic or initially tested positive in the prior 10 days.
- Individuals (all sex, all gender) at least 18 years of age and at most 65 years of age and in good oral health without any known allergies to commercial dental products or cosmetics.
- Evidence of a personally signed and dated informed consent document indicating the subject (or legally acceptable representative) has been informed of all pertinent aspects of the trial and all of their questions have been answered.
- Able to comprehend and follow the requirements of the study (including availability on scheduled visit dates) based on research site personnel’s assessment.

- Females of childbearing potential will have a negative urine pregnancy test (on site) or be physically incapable of pregnancy (implants or injections, Intrauterine device, Bilateral tubal ligation, Hysterectomy, Ovariectomy, Women post-menopausal)

4.2 Exclusion Criteria

Subjects presenting with any of the following will not be included in the study:

- Patients who have been eating or drinking within an hour of the study
- Patients under 18 years old and older than 65 years old
- Subjects presenting with and/or self-reporting any of the following will not be included in the study:
 - history of significant adverse effects following use of oral hygiene products such as toothpastes and mouth rinses. (self-reported)
 - Self-reported allergy to ethanol, essential oils (Eucalyptol, Menthol, Methyl salicylate, Thymol), Listerine, Cetylpyridinium Chloride, and other components in the mouth rinses.
 - History of serious medical conditions that, at the discretion of the Investigator, will disqualify the subject. (Self-reported)
 - A history of severe dry mouth (xerostomia), severe drug-induced xerostomia (antidepressants, anticonvulsants, antihypertensives), or Sjogren's syndrome
 - A history of recent (within the last 30 days) or current **recent oral herpes flare up**, candida (thrush) infection, aphous ulcer flare up, current/active severe periodontal disease, or other recent oral viral infection or flare up within the past 30 days (self-reported)
 - Current history of alcohol or drug abuse (self-reported).
 - History of drinking water or eating food within an hour of the study visit.
 - History of drinking alcohol within 12 hours of the study visit.
 - History of using a commercial mouth rinse within 24 hours of the study visit.
 - Participation in any study involving oral care products, concurrently or within the previous 30 days. (self-reported)
 - Positive pregnancy test, reported pregnancy or lactation (this criterion is due to oral tissue changes related to pregnancy and nursing which can affect interpretation of study results. Additionally, women are advised to check with their physician before using Ethanol rinses during pregnancy and lactation, which cannot occur in a blinded, randomized trial.)
 - Other severe acute or chronic medical or psychiatric condition or laboratory abnormality that may increase the risk associated with trial participation or investigational product administration or may interfere

with the interpretation of trial results and, in the judgment of the Investigator, would make the subject inappropriate for entry into this trial.

- Patient with developmental/cognitive disability that cannot self-consent, comprehend and follow the requirements of the study based on research site personnel's assessment.
- Patients with sizable mucosal tears, abrasions, growths or burns in the mouth
- The following table lists exclusion criteria specific to each mouth rinse proposed in the study:

mouth rinse*	Exclusions
26.9% ethanol plus essential oils	
 ● Do not use in children under 12
0.1% Cetylpyridinium Chloride	
 ● Do not use in children under 6
Sterile Water	No contraindications

**All mouth rinses are commercially available in the USA, routinely used in clinical settings, and will be used in an on-label manner.*

Summary of Inclusion and Exclusion Criteria for Mouth rinse RCT

Inclusion Criteria	Exclusion Criteria
Individuals (all sex, all gender) at least 18 years of age and at most 65 years of age in good oral health and with stable physical health, decided at the discretion of the study coordinator.	Known allergies or significant adverse reactions following the use of oral hygiene products (toothpastes, mouth rinses), commercial cosmetics, iodine, and any ingredient in the mouth rinses (list will be provided).

Diagnosed COVID+ status by physician, official testing site, or on-site rapid antigen test administered by study personnel at the time of visit. Either became symptomatic or initially tested positive in the prior 10 days.
	
Established history of severe Xerostomia (drug-induced or autoimmune dry mouth), severe periodontal disease with actively bleeding gums, significant oral abrasions/ulcers or growths, alcohol abuse, and/or recreational drug abuse. Other severe acute or chronic medical or psychiatric condition or laboratory abnormality that may increase the risk associated with trial participation or investigational product administration or may interfere with the interpretation of trial results and, in the judgment of the Investigator, would make the subject inappropriate for entry into this trial.


Evidence of a personally signed and dated informed consent document indicating the subject (or legally acceptable representative) has been informed of all pertinent aspects of the trial and all of their questions have been answered.
	
Drinking or eating within an hour of the study visit. Consuming alcohol within 12 hours of the study visit. Rinsing with a commercial mouth rinse within 24 hours of the study visit.

Able to comprehend and follow the requirements of the study (including availability on scheduled visit dates) based on research site personnel's assessment.
	
Developmental/cognitive disability such that patient cannot self-consent, comprehend and follow the requirements of the study based on research site personnel's assessment.

Females of childbearing potential will have a negative urine pregnancy test (on site) or be physically incapable of pregnancy (implants or injections, Intrauterine device, Bilateral tubal ligation, Hysterectomy, Ovariectomy, Women post-menopausal)
	
Positive pregnancy test, reported pregnancy or lactation.

	
A history of recent (within the last 30 days) or current recent oral herpes flare up, candida (thrush) infection, aphous ulcer flare up, current/active severe periodontal disease with bleeding gums, or other recent oral viral infection or flare up within the past 30 days.

4.3 Study Enrollment Procedures

Subjects will be recruited from patients seen in the UNC Respiratory Diagnostic Clinic (RDC), UNC testing sites or UNC hospital who have tested positive for COVID+. The subjects are being approached by phone or email based off of the UNC RDC/EPIC COVID+ list. Subjects will be contacted for recruitment by phone and (if unreachable by phone) by secure email by study personnel; patients will have the study rationale and risks explained and will be provided time to ask questions and consider participation. If patients are interested in participating, a single appointment will be scheduled for them at the Adams School of Dentistry

Go Health Clinical research core. Consent documentation will be signed in person and in private in the Go Health Clinical Research Core. For hospital in-patients appearing on the EPIC COVID+ list, subjects will be approached by a study coordinator in their private hospital room. The study's purpose and requirements will be explained and the patient will have the opportunity to ask questions and will have time to consider participation. If interested, consent forms will be left in the patient's room for review. Study team members will return later for final consent signatures and if consenting, the study visit can occur in their private room. For Spanish speaking patients and/or parents, Spanish forms will be provided and communication will occur through a Spanish translator. All patients are adults and over normal cognitive capacity, and therefore will be able to consent for themselves. A list of COVID+ subjects will be provided by the RDC clinic and UNC Epic, available via secure UNC servers and secure UNC email to our research team's clinical coordinator, and this list will include names and contact details (PHI). This list is updated daily and provided to approved research sites, including ours.

At the visit, a consented patient will answer screening questions regarding inclusion and exclusion criteria. Answers will be entered into the CDART research database managed by UNC. Participants lacking a lab or physician confirmed COVID+ test will be administered a rapid antigen test by study personnel at the time of their visit to confirm their COVID infection. Any participants that produce a negative rapid antigen test (on-site) will be excluded. Prior to finalizing these screening questions, women participants of childbearing potential will be asked to provide a urine sample in the restroom, to undergo a rapid pregnancy test by study personnel. Any pregnant or lactating patients will be excluded.

Our study statistician, [name], will create a block randomization schedule and perform these computations. All patients will be consented and then fill out our screening questions for inclusion and exclusion to confirm eligibility prior to being assigned to the randomization schedule.

5. STUDY INTERVENTIONS

5.1 Interventions, Administration, and Duration

Patients who meet all inclusion criteria without any exclusions will be asked to give a baseline salivary sample of 5ml over 5 minutes. The patient will then be asked to rinse with an unlabeled/blinded antiseptic mouth rinse for 60 seconds. Once s/he expectorates the mouth rinse, a time 0, 2ml salivary sample will be collected over 5 minutes. Then the patient will have 10 minutes to recuperate, while answering survey questions about their demographics and regarding the taste, color, flavor and acceptability of using the mouth rinse as part of routine dental and medical visits. Intra-oral photographs of notable lesions may be taken to document oral manifestations of COVID-19. At 15 minutes post-rinse, the patient will be asked to provide an additional 2ml saliva samples over 5 minutes,

followed by another 10 minute break. This sequence repeats for the 30, 45 and 60 minute time points. At 60 minutes, the patient will give their last salivary sample, and study participation will conclude. Participants will be provided with a gift card for their participation.

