1.3 Tertiary Objectives

The tertiary objective is to determine the acceptability of using antiseptic mouthwashes on reducing SARS-CoV-2 cellular infectivity by patients in various settings including healthcare contexts. *We hypothesize that patients will welcome the use of commercially available antiseptic mouth rinses into clinical practice.* All patients enrolled will be surveyed on the taste, appearance, sensation, and acceptability of using the mouth rinse in different settings. Understanding acceptability of a mouth rinse protocol is critical to implementation and therefore the ability to reduce COVID-19 transmission risk in clinical settings.

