6.2.2 Enrollment, Baseline, and/or Randomization

Enrollment

Outpatient subjects will be recruited from patients seen in the UNC Respiratory Diagnostic Clinic (RDC), UNC testing sites or UNC hospital who have tested positive for COVID-19. Subjects will be contacted for recruitment by phone and (if unreachable by phone) by secure email by study personnel; patients will have the study rationale and risks explained and will be provided time to ask questions and consider participation. If patients are interested in participating, a single appointment will be scheduled for them at the Adams School of Dentistry Go Health Clinical research core in the associated clinical research isolation area. Consent documentation will be signed in person and in private in the Clinical Research Core. A list of COVID+ subjects will be provided by the RDC clinic and EPIC, accessible via secure UNC servers or secure UNC email to our research team's clinical coordinator, and this list will include names and contact details (PHI). This list is updated daily and provided to approved research sites, including ours.

Baseline Assessments

Study personnel confirm enrollment qualifying criteria and perform a COVID rapid antigen test and pregnancy test on applicable individuals. Otherwise, there are no baseline assessments required as this study only requires a 70-90 minute single visit appointment.

Randomization

Our statistician will create a block randomization tool which will be provided to the unblinded study staff ([name]) to perform the randomization. In the instance that [name] is unavailable, [name] or [name] will perform randomization and set-up the rinses. The participant's group assignment will be communicated to the blinded clinical staff. All patients will be consented and then complete our screening questions for inclusion and exclusion to confirm eligibility prior to being assigned to the randomization schedule.

The researcher in charge of collecting the salivary samples will be blinded to the mouthwash solution, as they will be given a pre-aliquoted mouth rinse in an unlabeled storage tube to provide to the patient for the rinse.

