9. STATISTICAL CONSIDERATIONS

9.1 General Design Issues

A double-blinded, randomized controlled trial was chosen as the study design. It allows us to collect human based data on the effects of commercially available mouth rinses on salivary infectivity and viral load. A crossover study was not pursued because the repeated use of different mouth rinses is likely to confound the results. A 1-hour time-course was chosen to correspond with the average length of most dental procedures. Fifteen minute intervals were chosen to evaluate viral kinetics over time, and to see when infectivity rebounds post- mouth rinse.

Statistical Hypothesis

The central hypothesis of this study is that a 60 second antiseptic mouth rinse will effectively reduce viral infectivity (>50%) of SARS-CoV-2 for a minimum of 30 minutes duration.

The secondary hypothesis is that a 60 second mouth rinse will be well tolerated in a clinical care setting by a majority of patients and providers.

Sample Size Considerations

Based on our similar viral load studies evaluating mouth rinse efficacy against SARS-CoV-2 and other enveloped viruses, we used power calculations to estimate effect size and determine sample size as a function of length of mouth rinse time course.¹² With simultaneous comparisons, the sample size n=43 for each mouth rinse can detect the effect size in Cohen's $d = 0.8$, which is between medium and large, under 80% power and 0.016 type-I error rate by Bonferroni correction.¹² To account for 14% of patients having no virus in their saliva and 10% of patients producing insufficient saliva, we plan to enroll 55 participants per arm.

Statistical analysis of our deidentified data will be performed by [name], the statistician on this project.

Primary Outcomes

The analyses will compare viral RNA level (qRT-PCR) and viral infectivity levels between mouth rinse types and across the time course

Data generated from the qRT-PCR assays will be presented as mean standard deviation for normally distributed data and as median [Interquartile range] for non-normally distributed data. P values will be reported as two tailed. Between group comparisons will be performed using a Student's t test or Mann-Whitney U test. Normality will be assessed using the Kolmogorov-Smirnov test, and logistic regression will be performed with robust standard errors.

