9.4.3 Tertiary Outcomes

The tertiary objective is to determine the acceptability of using antiseptic mouthwashes on reducing SARS-CoV-2 cellular infectivity by patients in settings including healthcare contexts. *We hypothesize that patients will welcome the use of commercially available antiseptic mouth rinses into clinical practice.* All patients will be surveyed on the taste, appearance, sensation, and acceptability of using the mouth rinse in healthcare settings. Understanding acceptability of a mouth rinse protocol is critical to implementation and therefore the ability to reduce COVID-19 transmission risk in clinical settings.

Survey results will be evaluated using bivariate, descriptive statistics and non-parametric methods as appropriate for the question type. Outcome assessments will be conducted weeks to months after the study visit, when statistical analyses are conducted.

9.5 Data Analyses All data analyzed will be deidentified.

qRT-PCR: Data will be presented as mean standard deviation for normally distributed data and as median [Interquartile range] for non-normally distributed data. P values will be reported as two tailed. Between group comparisons will be performed using a Students t test or Mann-Whitney test. Normality will be assessed using the Kolmogorov-Smirnov test, and logistic regression will be performed with robust standard errors. Methods adapted from Bullard *et al* 2020.

Viral infectivity: The viral infectivity analysis will compare infectivity levels between mouth rinse types and across the time course for calculation of the reduction factor (RF). The RF will be calculated as the difference in the quotient of the infection titre before ('control titration') and after the mouth rinse ('remaining virus'). Therefore, the log10 titre and its (double) standard deviation (SD) were calculated as well as the variance of the RF.

Survey results will be evaluated using bivariate, descriptive statistics and non-parametric methods as appropriate for the question type.

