11.3 Participant Confidentiality

An Excel Linkage File key will be created with study ID (random alphanumeric code) to identify patients, saved in a secure folder in a UNC School of Dentistry (SOD) server, by the unblinded staff member. This linkage file will be stored separately from data and destroyed at the close of the study.. All data collected from participants and results from sample analysis will be coded with unique numerical

identifiers and stored in the UNC CDART clinical research database and on a secure UNC-CH server. Data will only be transmitted among the research team using the SOD secure research server. Demographic data will be transmitted among the research team through access to the secure CDART research database system, stored on secure UNC servers, which study personnel will access only through encrypted computers via secure user account. All research personnel will be trained in maintaining patient confidentiality and HIPAA.

Any data, specimens, forms, reports, and other records that leave the site will be identified only by a participant identification number (Participant ID, PID) to maintain confidentiality. We do not anticipate any data, specimens, forms reports and other records leaving the site as sample storage and analysis will occur on site. All paper records will be kept in a locked file cabinet, and all digital records will be stored in the encrypted, secure, password protected CDART research database. All computer entry and networking programs will be done using PIDs only. Information will not be released without written permission of the participant, except as necessary for monitoring by IRB, the FDA, the NCCIH, and the OHRP.

There is little to no potential for deductive disclosures from the survey portion of this study. Patients will be asked about the experience rinsing with a commercially available mouth rinse (such as Listerine). They will be asked to rate the taste, appearance/color, sensation, and their willingness to use the mouth rinse in the future. General demographics will be asked such as gender, race, ethnicity and age bracket. Their identity cannot be deduced from this information.

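### The plan does not provide for recording or using current ability to taste or smell, although people with active COVID-19 rate taste and flavour to judge acceptability for routine care

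*Combined protocol and SAP*

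**What the plan says.** **Who rates.** Only people with confirmed SARS-CoV-2 infection enter. Section 4.1 requires: "Either became symptomatic or initially tested positive in the prior 10 days". Section 3 admits both symptomatic and asymptomatic people.

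**What they rate.** Section 1.3 states: "All patients enrolled will be surveyed on the taste, appearance, sensation, and acceptability of using the mouth rinse in different settings". Section 9.4.3 repeats this for healthcare settings, and section 5.1 adds colour and flavour, with questions "regarding the taste, color, flavor and acceptability of using the mouth rinse as part of routine dental and medical visits". Sections 3 and 5.1 place the survey in the break after the first post-rinse saliva sample, so roughly 5 to 15 minutes after the rinse.

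**What the answer is for.** The hypothesis in section 1.3 is: "We hypothesize that patients will welcome the use of commercially available antiseptic mouth rinses into clinical practice". It sets no threshold. Section 9.1 words its secondary hypothesis differently, saying that a rinse "will be well tolerated in a clinical care setting by a majority of patients and providers".

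**What is recorded beforehand.** After the eligibility, antigen and pregnancy checks, section 6.2.2 says: "Otherwise, there are no baseline assessments required as this study only requires a 70-90 minute single visit appointment". Section 6.1 nevertheless schedules medical history, medications and vital signs at Visit 1, without giving their content. Section 10.2 names forms for eligibility, demographics and rinse experience. On demographics, section 11.3 says: "General demographics will be asked such as gender, race, ethnicity and age bracket".

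**How it is analysed.** Sections 9.1, 9.4.3 and 9.5 plan descriptive and two-variable summaries, with rank-type methods where suitable. None names taste or smell status.

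**The concern.** A taste or flavour rating depends on being able to taste and smell. The raters are ill with a respiratory infection, while the conclusion is meant for dental and medical patients in general. If some raters taste or smell abnormally, an arm's acceptability figure mixes two groups, and the one that matters for routine care is the group with normal function.

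Randomisation balances affected raters across rinses on average. It does not remove the effect on each arm's absolute acceptance, which is the quantity the hypotheses in sections 1.3 and 9.1 speak to. It also does not keep the difference between a strong-tasting rinse and water from shrinking if affected raters tell the two apart less well.

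The information is easy to obtain at the visit and hard to recover later: there is one visit and no follow-up (section 6.2.4), and the identifier link is eventually destroyed (section 10.2).

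**Working it through.** The plan gives no sample size, expected rate or power for acceptability, so there is no figure to reproduce. The check has a textual part and an illustrative part.

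**1. Where taste or smell status could appear**

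| Place | Content | Taste or smell status named? |
|---|---|---|
| 4.1, 4.2 eligibility | Infection, age, oral health, allergies, dry mouth, recent intake | No |
| 6.1 schedule | Includes medical history, content not given | No |
| 6.2.2 baseline | Eligibility, antigen and pregnancy tests | No |
| 10.2 forms | Eligibility, demographics, rinse experience | No |
| 11.3 demographics | Illustrative list of four items | No |
| 9.1, 9.4.3, 9.5 survey analysis | Descriptive, two-variable, rank-type | No |
| 15 appendices | Forms are held with the IRB application | Cannot be checked |

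**2. Size of the bias in one arm**

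Let q be the share of raters with altered taste or smell, and p_intact and p_affected the acceptance rates in the two groups. All three are assumptions.

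- Observed acceptance = (1 - q) × p_intact + q × p_affected
- Bias relative to people with normal taste = q × (p_affected - p_intact)

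| Assumed p_affected - p_intact | q = 10% | q = 30% | q = 50% |
|---|---|---|---|
| +20 points (taste reduced) | +2 | +6 | +10 |
| +45 points (taste reduced) | +4.5 | +13.5 | +22.5 |
| -20 points (taste distorted) | -2 | -6 | -10 |

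**3. Does it move a result across 50%?**

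The crossing point is q = (0.50 - p_intact) / (p_affected - p_intact).

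- 45% and 90%: 0.05 / 0.45 = 11%
- 45% and 75%: 0.05 / 0.30 = 17%
- 40% and 80%: 0.10 / 0.40 = 25%
- 60% and 90%: both lie above 50%, so no crossing
- 55% and 35% (distorted taste): 0.05 / 0.20 = 25%, with the pooled figure falling below 50% beyond that

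The answer is driven by the rates chosen.

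**4. Difference from water, one example**

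Assume water is accepted by 90% of all raters, and a strong rinse by 50% of intact and 90% of affected raters. The gap is then 40 × (1 - q) points: 36, 28 and 20 points at q = 10%, 30% and 50%. Normal-approximation power for two proportions (two-sided 5%) falls from over 99.9% at q = 0 to 91% at q = 50% with 84 per arm. With 55 per arm it falls from 99.8% to 75%. Both arm sizes stand in the documents: 84 in the précis and section 3, 55 in the sample-size text.

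**5. Precision if status is recorded**

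The worst-case 95% half-width is 1.96 × sqrt(0.25 / n).

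- All 84: 1.96 × sqrt(0.25 / 84) = 10.7 points
- Intact at q = 30%: n = 84 × 0.7 = 58.8, half-width 12.8 points
- Intact at q = 50%: n = 42, half-width 15.1 points
- With 55 per arm: 13.2 points overall and 15.8 points at q = 30% (n = 38.5)

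**The case against.** The strongest reply is that silence in the protocol does not prove silence in the forms. Section 15 says these sit with the IRB application, the demographic list in section 11.3 is only illustrative, and section 6.1 schedules a medical history at Visit 1 despite the sentence in section 6.2.2. Section 3 also says survey data will help identify clinical and other influences on how usable each rinse is, and two-variable analyses are planned. A reader might infer that taste status is never recorded and that the two groups can never be separated. The documents do not support that. What stands is narrower: no listed form or analysis names the variable, so nothing commits the trial to collecting or using it.

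Second, the documents never say that COVID-19 alters taste or smell, and section 3 gives no share with symptoms. Both the presence and the frequency of altered taste are therefore assumptions. This reply stands, and it limits the claim to a possible bias.

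Third, the direction is open. A reader might infer that acceptability must be overstated. Reduced taste would act that way if it makes a strong rinse less objectionable, but distorted taste could lower ratings.

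Fourth, ratings also cover appearance and willingness to use the rinse, which depend less directly on taste. This is fair, but taste and flavour are named items, and section 2.2 itself cites dislike of the flavour as a source of discomfort.

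**Conclusion.** The point holds as a gap in the plan for the acceptability outcome: current ability to taste or smell is neither planned as a variable nor used in the analysis, while taste and flavour ratings from people with active COVID-19 are carried over to routine care. Under the assumed ranges, an arm's acceptance could be misstated by +2 to +22.5 points if taste is reduced, or by -2 to -10 points if it is distorted. If no rater is affected, or if affected and intact raters accept equally, there is no bias.

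A reader might infer that a majority finding would be reversed at some particular share of affected raters. The documents do not support this. The crossing point moves with the assumed rates and can vanish, and the majority wording appears only in section 9.1, about tolerance, not in the acceptability hypothesis of sections 1.3 and 9.4.3.

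The infectivity and RNA outcomes are untouched. Acceptability is tertiary in section 1.3 and secondary in the précis and section 9.1. This is a cheap improvement to a lower-tier outcome, between optional and recommended.

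**What to change.** - **Collect.** Add one item to the Visit 1 forms, asked before the rinse so that the product does not colour the answer: current loss or change of taste or smell (none, partial, complete, distorted). List it in sections 6.1 and 6.2.2. If a form already asks this, say so there.
- **Analyse.** In sections 9.4.3 and 9.5, report acceptability by arm, overall and by that status.
- **Interpret.** When generalising to routine dental and medical visits, cite the result in participants without loss or change alongside the overall result.

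The cost is one question and one further split of the survey tables. The group without loss or change is smaller and its estimate less precise, as shown in step 5 of the working. The item would also supply the share of affected raters, which is now unknown. No visit, sample or laboratory procedure changes.
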